3.1.3 Statistical methods

For the primary safety endpoint, the Kaplan-Meier 12 month (365-day) primary safety event-free rate will be calculated. Subjects who withdraw from the study prior to 12 months without experiencing an event will be censored on the date of withdrawal. The 95% one-sided lower confidence limit of the observed safety event-free rate will be compared to the performance goal of 85%. If the lower confidence limit is greater than the performance goal, the null hypothesis will be rejected. The lower confidence limit will be calculated as the pointwise confidence limit using the log-log methodology.

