3.2.3 Statistical Methods

For the primary effectiveness endpoint, the Kaplan-Meier 12 month (365-day) primary effectiveness event-free rate will be calculated. Subjects who die or withdraw from the study prior to 12 months without experiencing an endpoint event will be censored on the date of death or the date of withdrawal. The 95% one-sided lower confidence limit of the observed primary effectiveness event-free rate will be compared to the performance goal of 50%. If the lower confidence limit is greater than the performance goal, the null hypothesis will be rejected. The lower confidence limit will be calculated as the pointwise confidence limit using the log-log methodology.

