5.2 Subgroup Analyses

An analysis will be performed for the primary endpoints to determine whether significant differences exist in endpoint results between subgroups. The list of covariates (with applicable subgroups in parentheses) includes the following:

- Sex (Female vs. Male)
- Age at time of consent (subjects > 60 years vs subjects \leq 60 years and subjects > 70 years vs subjects \leq 70)
- Repeat procedures in the blanking period (Repeat procedure within 90 days of index procedure vs. no repeat procedure within 90 days of index procedure)
- Ablation technique (PVI only vs. PVI + additional ablations)
- Use of device features (DirectSense used in the index procedure vs DirectSense not used in the index procedure).

Each subgroup covariate will be included as a single independent variable in a logistic regression model with the primary endpoint outcome as the dependent variable and a test for significance at the 15% level will be performed.

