5.3 Center Pooling Analysis

Center-to-center heterogeneity will be assessed for the primary endpoints by performing a random effects logistic regression analysis. Centers with less than five enrollments will be combined to form “supercenters”. Small centers will be combined until the newly created supercenter has five enrollments, and then a new supercenter will be created. Centers will be deemed to be heterogeneous if the variance of the random center effect is found to significantly differ from zero. A significance level of 15% will be used for this test.

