5.4 Catheter Type Pooling Analysis

Heterogeneity of outcomes by catheter type will be assessed for the primary endpoints by performing a logistic regression analysis with the primary endpoint outcome as the dependent variable and Catheter Type as the independent variable. Outcomes for the Blazer OI/IntellaNav OI catheters will be deemed to be heterogeneous with outcomes for the IntellaTip MiFi OI/IntellaNav MiFi OI catheters if no statistical association is found between catheter type and the primary endpoint outcomes through the logistic models. A significance level of 15% will be used for this test.

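### Subgroup, center and catheter-type tests use logistic regression on a 12-month outcome that is undefined for censored subjects, so they do not match the Kaplan-Meier primary analyses and can be distorted if dropout differs between groups

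*SAP*

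**What the plan says.** SAP 3.1.3 defines the safety result as a survival estimate: "the Kaplan-Meier 12 month (365-day) primary safety event-free rate will be calculated", and "Subjects who withdraw from the study prior to 12 months without experiencing an event will be censored on the date of withdrawal". SAP 3.2.3 does the same for effectiveness and adds deaths to the censoring rule: "Subjects who die or withdraw from the study prior to 12 months without experiencing an endpoint event will be censored".

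The group comparisons switch method. In SAP 5.2 each covariate is "included as a single independent variable in a logistic regression model with the primary endpoint outcome as the dependent variable". The level is fixed in the same section, at 15%. SAP 5.3 assesses center heterogeneity by "performing a random effects logistic regression analysis", and SAP 5.4 assesses catheter type by "performing a logistic regression analysis with the primary endpoint outcome as the dependent variable and Catheter Type as the independent variable", both also at 15%. Protocol 9.3.2 to 9.3.4 carry the same text.

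SAP 5.6.1 and 5.6.2 do separate subjects with complete 12-month data from those who left early without an event, and call the latter missing. That rule is written for the tipping-point analyses only. Sections 5.2 to 5.4 neither repeat it nor refer to it.

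**The concern.** Logistic regression needs a yes or no for every subject it uses. A subject censored before day 365 has neither. The programmer must exclude that subject, code the subject event-free, or code the subject as an event. The three choices give different event proportions, and none is specified, so two programmers following the same SAP could report different p-values.

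Exclusion overstates event rates, because early events stay in while event-free leavers drop out. Event-free coding understates them. If two groups lose subjects at different rates, the error differs by group, and a difference can appear where true event rates are equal. At stake is how far one can trust the only stated heterogeneity criteria for centers and catheter families in an FDA-mandated post-approval study, and whether those results agree with the Kaplan-Meier rates reported beside them.

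**Working it through.** **Inputs from the SAP.** Attrition 7.5% per year; expected event-free rates 90% (safety) and 60% (effectiveness); 329 and 183 TREATMENT subjects (3.1.2, 3.2.2); test level 15% (5.2 to 5.4).

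**Assumptions not in the documents.** Two-sided test (critical value 1.4395); 329 subjects in two equal groups of 164.5; exponential dropout unrelated to outcome; effectiveness events uniform over days 91–365; safety events within 7 days; the same true event rate *p* in both groups.

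**The plan's own figures.** Take the smallest exact-binomial N from which power stays at or above 80%, divided by 0.925:
- safety: 304/0.925 = 328.6, so 329
- effectiveness: 169/0.925 = 182.7, so 183
- secondary: 76/0.925 = 82.2, so 83

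All three match. The plain normal approximation gives 283/0.925, so 306, for safety.

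**Step 1: subjects with no defined outcome.** With 12-month dropout *d*, a subject whose event would fall on day *t* leaves first with probability 1 − (1 − d)^(t/365). Let *q* be its average over event times. The undefined share is u = p·q + (1 − p)·d.
- Effectiveness, d = 7.5%, q = 0.0474: 0.40 × 0.0474 + 0.60 × 0.075 = 0.0640; × 329 = 21.0 subjects.
- Safety, q = 0.0007: 0.10 × 0.0007 + 0.90 × 0.075 = 0.0676; × 329 = 22.2 subjects.

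**Step 2: what the logistic model sees.** Observed events are o = p(1 − q). The event proportion is *o* if censored subjects are coded event-free, o/(1 − u) if excluded, and o + u if coded as events.

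| Endpoint | Kaplan-Meier | Event-free | Excluded | As events |
|---|---|---|---|---|
| Effectiveness | 40.0% | 38.1% | 40.7% | 44.5% |
| Safety | 10.0% | 10.0% | 10.7% | 16.8% |

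**Step 3: rejection when true rates are equal.** For one binary covariate the logistic test is close to a two-proportion test. With event proportions *a* and *b*, D = |a − b| / √[a(1 − a)/n₁ + b(1 − b)/n₂], and the rejection probability is Φ(D − 1.4395) + Φ(−D − 1.4395).

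Example: effectiveness, dropout 5% vs 15%, coded event-free. q = 0.0315 and 0.0960, so o = 0.3874 and 0.3616. The standard error is 0.0533 and D = 0.484. Rejection = Φ(−0.956) + Φ(−1.923) = 0.170 + 0.027 = 19.7%.

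Rejection by coding (event-free / excluded / as events):

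| Dropout | Effectiveness | Safety |
|---|---|---|
| 7.5% vs 7.5% | 15.0 / 15.0 / 15.0% | 15.0 / 15.0 / 15.0% |
| 5% vs 10% | 16.2 / 15.2 / 21.0% | 15.0 / 15.4 / 37.1% |
| 5% vs 15% | 19.7 / 15.7 / 37.0% | 15.0 / 16.8 / 74.4% |
| 4% vs 20% | 26.9 / 16.7 / 62.3% | 15.0 / 19.7 / 96.6% |

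**Step 4: sensitivity to event timing.** Use a constant hazard over the year instead, with λe = −ln 0.60 = 0.5108, λd = −ln(1 − d) and o = λe/(λe + λd) × [1 − 0.60(1 − d)]. At 5% vs 15%, o = 0.3908 and 0.3717, and rejection is 17.6% event-free or 16.4% excluded. At 4% vs 20%, o = 0.3926 and 0.3619, and rejection is 21.6% or 18.7%.

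Simulation gave 18–19% event-free and 17% excluded at 5% vs 15%, and 23–24% and 17–18% at 4% vs 20%. The event-free figures lie between the two timing assumptions, and the excluded figures agree with them to within about a point.

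**Step 5: the alternative.** In simulation, with dropout from equal up to 5% vs 20%, a 12-month Kaplan-Meier log-log comparison rejected 13.9–15.4% of the time. Log-rank behaved similarly (14–16%).

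**The case against.** The strongest reply is that one sentence is missing and little else. SAP 5.6 already treats early leavers as missing, and logistic software omits a missing response. Under exclusion the inflation is at most about four points for effectiveness, and about five for safety even at 4% vs 20%. For a supportive screen at a liberal 15%, analysed after all 12-month data are in (SAP 5.1), that is tolerable, and a fixed 12-month binary outcome is defensible once its coding is stated. Most of this stands as a limit on size. It does not close the gap, because 5.2 to 5.4 do not adopt the 5.6 rule, and event-free coding is an equally available reading.

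A further objection concerns the remedy. Cox and log-rank compare hazards over all follow-up, whereas the primary estimand is the rate at day 365. Effectiveness combines acute failure with recurrence counted only from day 91, so proportional hazards is doubtful. This is correct, and it is why a 365-day Kaplan-Meier difference is preferred.

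A reader might infer three stronger things that the documents do not support:
- That these tests do confuse dropout with outcome. This needs differential dropout, and the documents give only the overall 7.5%.
- That they decide whether data are pooled. SAP 5.3 and 5.4 attach no action to a heterogeneous result, and SAP 5.5 reports results by catheter type regardless.
- That the logistic results cannot be reconciled with Kaplan-Meier. At planned attrition, 40.0% becomes 38.1% or 40.7% unless censored subjects are coded as events, and a footnote could explain that.

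**Conclusion.** The concern holds as a gap in specification and a mismatch of method. The dropout artefact is a possibility, not an established fault. About 21 to 22 of 329 subjects would have no defined outcome. With equal dropout there is no inflation. With unequal dropout, effectiveness rejection at the nominal 15% rises to about 18–19% (event-free) or 17% (excluded) at 5% vs 15%, and to about 23–24% or 17–18% at 4% vs 20%; event timing shifts these by up to about three points. Safety stays near 15% if censored subjects are coded event-free and events fall in the first week. Coding censored subjects as events would distort both endpoints badly, but nothing in the SAP points to that choice.

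These sizes rest on an equal split, independent dropout and assumed differentials. They cover the two-group tests; the center random-effect test was not quantified. The primary pass/fail tests, their power and the sample size do not use these models and are unaffected. A correction is worth making before analysis, at the level of a recommended change.

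**What to change.** In SAP 5.2 and 5.4 (and Protocol 9.3.2 and 9.3.4), compare groups using the primary analysis's event and censoring dates. The preferred test is the difference in 365-day Kaplan-Meier rates on the log-log scale, which matches the primary estimand; a log-rank or Cox test is acceptable. In SAP 5.3 (Protocol 9.3.3), use a time-to-event model with a random center effect (frailty). Report 12-month Kaplan-Meier rates with log-log limits for each group. Keep logistic regression as a sensitivity analysis, and state how subjects censored before day 365 are coded.

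State also whether ATTEMPT subjects enter the safety models. They are in the safety tipping-point cohort (SAP 5.6.1) but are followed for one month only (Protocol 7.3), so their 12-month outcome would be undefined too.

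The cost is SAP wording and a little programming, with no new data. The drawback of Cox or log-rank is that they compare hazards over all follow-up and not the day-365 rate. None of these methods removes bias from outcome-related withdrawal, such as the withdrawal before a repeat ablation with a non-study catheter that Protocol 8.14 permits.

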5.3 Center Pooling Analysis

Center-to-center heterogeneity will be assessed for the primary endpoints by performing a random effects logistic regression analysis. Centers with less than five enrollments will be combined to form “supercenters”. Small centers will be combined until the newly created supercenter has five enrollments, and then a new supercenter will be created. Centers will be deemed to be heterogeneous if the variance of the random center effect is found to significantly differ from zero. A significance level of 15% will be used for this test.

5.4 Catheter Type Pooling Analysis

Heterogeneity of outcomes by catheter type will be assessed for the primary endpoints by performing a logistic regression analysis with the primary endpoint outcome as the dependent variable and Catheter Type as the independent variable. Outcomes for the Blazer OI/IntellaNav OI catheters will be deemed to be heterogeneous with outcomes for the IntellaTip MiFi OI/IntellaNav MiFi OI catheters if no statistical association is found between catheter type and the primary endpoint outcomes through the logistic models. A significance level of 15% will be used for this test.

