## **3. Device Description**

### ***3.1. Open-Irrigated Ablation Catheters***

The study will include the following Boston Scientific Open-Irrigated Catheters in geographies where commercially approved for PAF ablation:

- Blazer Open-Irrigated Ablation Catheter (Blazer OI)
- IntellaNav Open-Irrigated Ablation Catheter (IntellaNav OI)
- IntellaNav MiFi Open-Irrigated Ablation Catheter (IntellaNav MiFi OI)
- IntellaTip MiFi Open-Irrigated Ablation Catheter (IntellaTip MiFi OI)

The BSC Open-Irrigated catheters are designed to deliver RF energy to catheter tip electrode for cardiac ablation. The BSC OI catheters incorporate an open-irrigated cooling mechanism through a tip that is partitioned into two chambers. The proximal chamber circulates normal saline (0.9 %) within the tip to cool the proximal electrode and mitigate overheating while the distal chamber allows the fluid to flow through six irrigation holes into the patient's vasculature, thereby cooling the tip/tissue interface. A luer connection at the proximal end of

the handle connects the catheter to an Irrigation Tubing Set, allowing an Irrigation Pump to generate the flow of saline to the catheter.

The electrode segment of the catheters is comprised of a tip electrode and three ring electrodes. The tip electrode of all the BSC OI catheters has an embedded temperature sensor and delivers RF energy for cardiac ablation. Additionally, the IntellaTip MiFi OI and the IntellaNav MiFi OI include three mini-electrodes in the catheter tip to provide high-resolution electrograms (EGM) and the IntellaNav OI and the IntellaNav MiFi OI catheters include a position sensor for magnetic tracking and navigation of the catheter on a Rhythmia Mapping System. The ring electrodes record EGM signals for mapping and deliver stimulus for pacing. The catheters interface with standard RF generators through the Rhythmia Connection Box. The catheter handle includes the electrical connector for the cable connection to the Connection Box and one luer fitting used to connect the catheter to the Irrigation Tubing Set.

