### ***3.2. Rhythmia Mapping System***

The Rhythmia™ Mapping System, the Rhythmia HDx Mapping System, and the IntellaMap Orion™ mapping catheter are designed for electroanatomical mapping in catheter ablation procedures. The Rhythmia Mapping System tracks catheters inside the heart in order to visualize their location and construct geometric shells. The Rhythmia Mapping System is also capable of using intra-cardiac location and electrical information to display electroanatomical maps - electrical activity information on the constructed geometry. Such electrical information can be visualized in 3D and in color. The commercially available system operates the latest commercially-available software (version 1.4 or newer). Rhythmia HDx equipped with software version 2.0 may include the DirectSense feature. This feature allows for an impedance-based metric that can be used in conjunction with other clinical diagnostic measures (e.g., electrogram amplitude, fluoroscopy, intracardiac echocardiography, magnetic and impedance navigation, and tactile feedback) to inform catheter stability and navigation within the heart.

Subsequent versions of the Rhythmia Mapping System (including but not limited to the already commercially released upgrade, the Rhythmia HDx) and software may be used during this study as they become commercially available after regulatory approval in their geography.

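### The catheter-type and DirectSense tests leave center out of the model, so center differences can appear as device differences if device use clusters by center

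*SAP*

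**What the plan says.** The catheter-type check in SAP 5.4, repeated in Protocol 9.3.4, is carried out by "performing a logistic regression analysis with the primary endpoint outcome as the dependent variable and Catheter Type as the independent variable". Its level is fixed: "A significance level of 15% will be used for this test". DirectSense is one row of the subgroup list in SAP 5.2 and Protocol 9.3.2, with the contrast "DirectSense used in the index procedure vs DirectSense not used in the index procedure". The rule for that list is: "Each subgroup covariate will be included as a single independent variable in a logistic regression model", again at 15%.

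Center is handled in a different place. SAP 5.3 states: "Center-to-center heterogeneity will be assessed for the primary endpoints by performing a random effects logistic regression analysis". That model merges centers with fewer than five enrollments into supercenters, and it is not linked to either device model. SAP 5.5 adds primary endpoint results stratified by catheter family, not by center.

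Several passages describe how a device comes to be used. Catheters enter the study "in geographies where commercially approved for PAF ablation" (Protocol 3.1). Protocol 8.5 leaves the ablation workflow to the physician's preference. On the mapping side, "Rhythmia HDx equipped with software version 2.0 may include the DirectSense feature" (Protocol 3.2), while the synopsis also admits the first-generation system and software from version 1.4. The study is non-randomized.

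**The concern.** A single-covariate logistic model treats all subjects as independent and equally likely to receive either device. The documents give reasons to doubt both. Local approval, the installed mapping system and the operator's habits act at center level, so subjects at one center may share both a device and a center-specific outcome rate. The plan itself allows for center differences: it caps each site at 41 subjects, tests center heterogeneity, and reports outcomes by center experience in the earlier IDE study. That last factor is defined by prior use of the Blazer OI catheter, which is one of the devices being compared.

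Two things can then go wrong. The standard error of the device effect is too small, so the test rejects more often than 15%. And a real device effect cannot be told from a center effect in either direction. DirectSense has a further difficulty: the not-used group can include procedures on systems that did not offer the feature, so the contrast may mix feature use with system generation.

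What is at stake is how the pooling check for two catheter families under separate PMA supplements (Protocol 2.2) is read, and how the DirectSense subgroup result is read.

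**Working it through.** **Inputs from the documents.** 329 TREATMENT subjects (SAP 3.1.2). 25-50 centers, at most 41 subjects each (SAP 1.5). Expected event-free rates of 90% for safety and 60% for effectiveness (SAP 3.1.2, 3.2.2), so event rates of 10% and 40%. Test level 15%; sidedness is not stated and is taken as two-sided, which gives a critical value of z(0.925) = 1.44.

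**Inputs assumed.** Between-center SD on the logit scale of 0, 0.3, 0.5 or 0.7. With ICC = SD²/(SD² + π²/3), these are latent intraclass correlations of 0, 0.03, 0.07 and 0.13. Device use is either one type per center, an 85/15 split by center preference, or 50/50 in every center. Center sizes are unequal. There is no true device effect.

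**Step 1: reproduce the 15%.** A Wald test of the single-covariate model, 4,000 simulated trials per cell, has a Monte Carlo standard error of √(0.15 × 0.85/4000) = 0.6 percentage points. With center SD 0 it rejects in 14.0-15.8%. With devices split evenly in every center it also rejects in 14.0-15.8%, whatever the SD. The nominal level holds in both situations.

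**Step 2: let device use cluster by center.** Rejection rates (%) at SD 0.3 / 0.5 / 0.7:

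| Endpoint | Centers | One device per center | 85/15 by preference |
|---|---|---|---|
| Effectiveness | 25 | 22.5 / 30.1 / 38.6 | 17.8 / 24.1 / 28.2 |
| Effectiveness | 50 | 18.5 / 24.9 / 30.7 | 16.5 / 18.7 / 23.5 |
| Safety | 25 | 17.9 / 22.0 / 27.4 | 15.8 / 18.8 / 21.6 |
| Safety | 50 | 16.3 / 18.9 / 21.9 | 16.0 / 17.4 / 18.5 |

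**Step 3: check by formula.** With one device per center:

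- Actual level = 2 × [1 − Φ(1.44/√D)].
- Design effect D = 1 + [(1 + c²)m − 1]ρ, where m is the mean center size and c² the squared coefficient of variation of center size, assumed 1/3.
- On the scale of the observed outcome, ρ is roughly SD² × p(1 − p).

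For 25 centers, m = 329/25 = 13.16 and (4/3)(13.16) − 1 = 16.55. At SD 0.5:

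- Effectiveness: ρ = 0.25 × 0.4 × 0.6 = 0.060; D = 1 + 16.55 × 0.060 = 1.99; level = 30.8% (simulated 30.1%).
- Safety: ρ = 0.25 × 0.1 × 0.9 = 0.0225; D = 1 + 16.55 × 0.0225 = 1.37; level = 21.9% (simulated 22.0%).

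The formula also shows why safety suffers less: p(1 − p) is 0.09 rather than 0.24.

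**Step 4: account for center.** Under the 85/15 split, a center-stratified (Cochran-Mantel-Haenszel) test rejects in 14.4-16.0%. With one device per center, a center-clustered comparison rejects in 15.3-19.1%. The second figure stays somewhat high because only between-center information is left. A fitted random-intercept model was not itself simulated.

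**Step 5: read the SAP 5.4 rule.** As written, the two families are called heterogeneous when no association is found. Taken literally, a spurious association would label them not heterogeneous. The excess rejections in Step 2 therefore become false claims of heterogeneity only once the rule is put the right way round.

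**The case against.** A reader might infer that device use is essentially fixed by center and that the true error is therefore well above 15%. The documents do not support that. They give no between-center variance and no device mix by center. Protocol 5.3 describes all four catheters as FDA-approved for PAF and allows any of them once locally available, and at least half the sites are to be in the US, so geography need not restrict choice at those sites. Physician preference is compatible with variation within a center. Protocol 3.2 lets systems and software be upgraded during the study, so one center can contribute procedures with and without DirectSense. These points stand, and the size of the problem must be stated as conditional.

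A reader might also infer that study conclusions are at risk. They are not: SAP 3 and 4.3 rest success on the two Kaplan-Meier primary tests. No document attaches an action to the device tests, and SAP 5.5 reports results by catheter family whatever the test shows.

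Two limits on the remedy also stand. Safety expects about 0.10 × 329 = 33 events over 25-50 centers, which is thin for a random intercept, a device term and region terms together. Where each center uses one device, no model fully separates the two. In addition, SAP 5.7 sends further DirectSense analysis to a separate plan that was not among the documents reviewed, so whether that plan adjusts for center is unknown. SAP 5.2 nevertheless prespecifies its own unadjusted DirectSense test.

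**Conclusion.** The concern holds in conditional form. Both device models omit center in a non-randomized study where device use can follow center. Over the assumptions tried, the nominal 15% test runs from about 15% (no center variance, or even mixing within centers) to about 39% (one device per center, logit SD 0.7, 25 centers, effectiveness). For safety with 50 centers and one device per center it is about 16-22%. The direction is secure and the amount is not, because it depends on a center variance and a device mix that the plan does not give. The same figures apply to DirectSense only so far as its use clusters by center in the same way.

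The reversed rule in SAP 5.4 is a separate defect in the same section. Correcting it does not supply the missing center term. Since the tests lie outside the success rule, this is a cheap improvement of low-to-moderate severity.

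**What to change.** - In SAP 5.4/Protocol 9.3.4 and the DirectSense row of SAP 5.2/Protocol 9.3.2, include center as a random intercept or as a stratum. Use actual centers rather than the supercenters of SAP 5.3 where feasible, since a merged center can mix device types.
- Add region (US, Europe, Asia-Pacific) only if event counts allow; for safety they may not.
- Tabulate device use by center and region. Report the within-center comparison from centers that used both types, and state that device and center cannot be separated in the rest.
- Where system generation and software version are available, also show the DirectSense comparison among capable systems only. The Protocol 8.5 data list names catheter models and use of Rhythmia features but not these two items, so availability must be confirmed first.
- Correct the SAP 5.4/Protocol 9.3.4 rule so that finding an association, not its absence, indicates heterogeneity.

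The cost is SAP and protocol wording and a little programming, with no new subjects or visits. The downside is wider intervals when a device is used at few centers, and possible convergence problems for safety; the stratified test is the fallback.

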### 9.3.4. Catheter Type Pooling Analysis

Heterogeneity of outcomes by catheter type will be assessed for the primary endpoints by performing a logistic regression analysis with the primary endpoint outcome as the dependent variable and Catheter Type as the independent variable. Outcomes for the Blazer OI/IntellaNav OI catheters will be deemed to be heterogeneous with outcomes for the

IntellaTip MiFi OI/IntellaNav MiFi OI catheters if no statistical association is found between catheter type and the primary endpoint outcomes through the logistic models. A significance level of 15% will be used for this test.

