4 GENERAL STATISTICAL METHOD

4.1 Analysis Sets

While each endpoint was individually powered, each endpoint analysis will use all available data from all eligible subjects, regardless of original calculated sample size.

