5 ADDITIONAL DATA ANALYSES

5.1 Interim Analyses and Progress Report Content

No formal interim analyses are planned for the purpose of stopping the study early for declaring effectiveness or for futility. Analysis of each endpoint will be performed when all applicable data for that endpoint has been collected. Analysis of the 12-month endpoints (Primary Safety, Primary Effectiveness, Secondary Effectiveness and all additional analyses pertaining to these endpoints) will be included in a Primary Endpoint Report. Additionally, Kaplan-Meier analyses for the Primary Safety Endpoint events using all available data at the time of the report will be included in interim progress reports to the FDA. These analyses will use the same definition of safety events used in the Primary Safety Endpoint but will censor active subjects who have not experienced an endpoint event and have not completed their 12-month follow-up on the day of the data snapshot.

Progress reports will be provided to the FDA every 6 months for the first two years and annually thereafter. Reports will include sections outlined in the relevant FDA guidance pertaining to Post Approval Studies. At minimum, the progress reports will contain the following:

- Number of study sites with enrolled subjects
- Summary of subject enrollment, subject status, and demographics
- Analysis of Primary Safety Endpoint events
- Summary of adverse events, deaths, deviations, and device deficiencies

Results from the progress reports will be posted on the FDA PAS website (https://www.accessdata.fda.gov/scripts/cdrh/cfdocs/cfPMA/pma_pas.cfm).

Field Code Changed

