5.5 Additional Analyses

An analysis will be done for each primary endpoint stratifying results by catheter type (Blazer OI/IntellaNav OI and IntellaTip MiFi OI/IntellaNav MiFi OI).

Additional analyses will also be done to characterize the procedural workflow data in AF ablation cases with the Rhythmia Mapping System. Procedural workflow data will include, but not be limited to:

- electro-anatomical mapping information
- ablation gap detection (including gap detection techniques)
- ablation techniques (including use of DirectSense)

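### The catheter-type heterogeneity rule runs backwards in both protocol and SAP: the two families are called heterogeneous when the 15% test finds no association

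*SAP*

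**What the plan says.** SAP 5.4 sets out to assess whether outcomes differ by catheter type. For each primary endpoint it fits a logistic regression with catheter type as the independent variable and tests it at 15%. Its decision rule for the Blazer OI/IntellaNav OI family reads "deemed to be heterogeneous with outcomes for the IntellaTip MiFi OI/IntellaNav MiFi OI catheters if no statistical association is found between catheter type". The other side of that association is the result on each primary endpoint.

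Protocol 9.3.4 gives the same heterogeneous label under the same condition: "catheters if no statistical association is found between catheter type and the primary endpoint outcomes through the logistic models".

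The section just before it in each document (SAP 5.3, protocol 9.3.3) deals with centers, also at 15%: "Centers will be deemed to be heterogeneous if the variance of the random center effect is found to significantly differ from zero".

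Two other places fix the consequences. SAP 5.1 says that the 12-month endpoint analyses and "all additional analyses pertaining to these endpoints) will be included in a Primary Endpoint Report". SAP 5.5 adds, without any condition: "An analysis will be done for each primary endpoint stratifying results by catheter type".

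**The concern.** Heterogeneity by catheter type means that the outcome depends on catheter type, which is what a significant association in the logistic model would show. Both documents attach the label to the opposite result. Because they share the sentence, neither corrects the other, and no other section does so.

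The question is a real one for this study. It serves as the post-approval study for all four catheters (protocol sections 4 and 5), the MiFi catheters came in under a separate supplement (protocol 2.2), and success is judged on the combined family (protocol 9.1, SAP section 3). This is the only planned test of whether the two groups behave alike. Applied literally, the rule would put the reverse of the intended verdict into the Primary Endpoint Report. Applying the sensible direction without saying so would be an undocumented departure from the plan.

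**Working it through.** The documents give no figure to reproduce here. The check is of the rule's direction, then of what the rule does when followed.

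**Direction**

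| | Center rule (SAP 5.3, protocol 9.3.3) | Catheter rule (SAP 5.4, protocol 9.3.4) |
|---|---|---|
| Null hypothesis | Variance of the center effect is zero | No association of catheter type with outcome |
| Level | 15% | 15% |
| Null rejected | Heterogeneous | Not labelled heterogeneous |
| Null not rejected | Not labelled heterogeneous | Heterogeneous |

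The two rules have the same structure and opposite labels. The center rule agrees with the stated aim of the catheter section; the catheter rule does not.

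**Inputs**

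- Level 15% (SAP 5.4). Sidedness is not stated; two-sided is assumed, so the critical value is z = 1.4395.
- N = 329 TREATMENT subjects (SAP 3.1.2). As a second case, 304 completers: 329 × (1 − 0.075) = 304.3, using the planned 7.5% attrition. This assumes that censored subjects drop out of the logistic model.
- Catheter split and true gap between families: not in the documents, so assumed. Splits are even (164/165) and 80:20 of 304 (243/61). The gaps are centered near the expected rates of 60% (effectiveness) and 90% (safety).

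**Formulas**

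P(heterogeneous as written) = 1 − P(association found).

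P(association found) ≈ Φ[(d − z·s₀)/s₁] + Φ[(−d − z·s₀)/s₁], where d = |p₁ − p₂|, s₀ = √[p̄(1 − p̄)(1/n₁ + 1/n₂)] with p̄ the pooled rate, and s₁ = √[p₁(1 − p₁)/n₁ + p₂(1 − p₂)/n₂].

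**Identical families.** P(association found) = 0.15, so the written rule declares heterogeneity with probability 1 − 0.15 = 0.85 at any split.

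**One case in full: effectiveness 65% vs 50%, 164/165**

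- p̄ = (164 × 0.65 + 165 × 0.50)/329 = 0.5748
- s₀ = √[0.5748 × 0.4252 × (1/164 + 1/165)] = 0.0545
- s₁ = √[0.2275/164 + 0.25/165] = 0.0539
- First term: (0.15 − 1.4395 × 0.0545)/0.0539 = 1.328 (unrounded inputs), Φ = 0.908. The second term is negligible.
- P(heterogeneous as written) = 1 − 0.908 = 0.092

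**All cases: probability of the heterogeneous label under the written rule**

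| True rates | 329, even split | 304, 80:20 split* |
|---|---|---|
| Identical | 0.850 | 0.850 |
| Effectiveness 65% vs 55% | 0.339 | 0.495–0.510 |
| Effectiveness 65% vs 50% | 0.092 | 0.241–0.247 |
| Safety 92.5% vs 87.5% | 0.470 | 0.556–0.652 |
| Safety 95% vs 85% | 0.054 | 0.160–0.198 |

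*The range covers which family has the higher rate.

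With the direction corrected, each entry becomes one minus itself: 0.150 for identical families and 0.908 for the case worked above.

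A simulation of 200,000 logistic likelihood-ratio tests at the even split of 329 gave 0.341, 0.095, 0.465 and 0.045 for the four gaps in table order. For identical rates it gave 0.854 (60%) and 0.849 (90%). The approximation is adequate.

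**The case against.** The strongest reply is that this is a drafting slip without consequences. The section's purpose and the neighboring center rule make the intent plain, and a competent analyst would probably apply the test the right way round. No action follows from the verdict: success depends only on the two performance-goal tests (SAP section 3 and 4.3), and results by catheter family are shown whatever the label says. Apart from the 85%, which is simply 1 − 0.15, every probability rests on an assumed split and gap. How often truly different families escape the label also depends on the split: with 95:5 of 329 (313/16), the same formula gives 0.58 to 0.61 even for 65% against 50%. Finally, the slip may have been the word heterogeneous written for homogeneous, so more than one repair is possible.

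Most of this stands, and it limits the weight of the point. It does not remove it. The sentence is a stated decision rule, it is complete, and it is the same in both documents. The reversal bites only if the rule is followed literally, but following the plan literally is what a pre-specified rule is for. A report that sets stratified results beside a reversed verdict would contradict itself.

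**Conclusion.** The concern holds. As written, the rule in SAP 5.4 and protocol 9.3.4 returns the complement of the intended conclusion for each primary endpoint. Identical families are called heterogeneous 85% of the time instead of 15%; this figure needs only the 15% level. In every assumed scenario examined, identical families are more likely to receive the label than different ones. The exact probabilities for different families depend on the assumed split, gap and two-sided test.

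The point should be fixed, but it does not threaten the main result. The tests against 85% and 50%, the type I error control, the sample size and the success rule are untouched.

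**What to change.** In SAP 5.4 and protocol 9.3.4, change the condition so that the two families are deemed heterogeneous *if a statistical association is found (p<0.15)* between catheter type and the primary endpoint outcome. Leave the success rule and the planned stratified reporting as they are.

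Calling the families homogeneous when no association is found would also restore the direction. Declaring heterogeneity on a significant association is better: it matches the center rule, and a non-significant test does not show that the families are alike.

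The cost is one sentence in each document, with no new data and no burden on subjects. SAP section 6 and protocol 9.3.6 already provide for an amended SAP approved before the analyses are run. Protocol 12.3 requires ethics review of any protocol amendment, so the SAP can be corrected first and the protocol sentence aligned at its next amendment.
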